**Change 20:**

Added that IVRS / IWRS procedures can be found in the IVRS / IWRS manual.

***Section 7.1.2.2 Initial visit-Dose 1, Day 1 (Treatment Arms A, B, and C):***

Last paragraph, 2nd sentence:

Added text:

The order date for the next dose cannot be earlier than the pre-defined country lead time, see IVRS / IWRS manual.

**Change 21:**

Changed the terminology for “active safety follow-up” period to “active follow-up” period since efficacy assessments are also included in these visits. In addition, the terminology for “extended active follow-up” period was changed to “long-term follow-up” period; this change was done to ensure the use of a consistent term across the radium-223 program.

- Synopsis - Methodology
- Section 4.1 Design overview
- Section 6.8 Post-study therapy
- Section 7.1.1 Tabulated overview, Table 7-1 Schedule of procedures
- Section 7.1.2.6 Active follow-up
- Section 7.1.2.7.1 End of active follow-up with clinic visits
- Section 7.1.2.7.2 End of active follow-up without scheduled clinic visits
- Section 7.1.2.8 Long-term follow-up to 7 years following last dose
- Section 7.1.2.8.1 Long-term follow-up (via telephone follow-up)

- Section 7.1.2.8.2 End of long-term follow-up
- Section 8.4.4 Safety analysis

**Change 22:**

***Section 7.3.2 Definition of efficacy variables:***

3rd sentence:

New text:

Details on definitions of starting points and baselines will be provided in the SAP or in the imaging charter or other central reviewer documentation.

***Section 7.3.4.3 Radiological progression endpoints:***

1st paragraph, 2nd sentence:

Old text:

Assessment of radiological progression will be made ~~at the site level.~~

New text:

Assessment of radiological progression will be made by independent central review.

3rd paragraph:

New text:

The central reviewer will determine the applicable baseline values for and assess radiological progression with respect to each applicable baseline.

4th paragraph:

Added text:

Further details will be defined in the imaging charter and / or related central review documentation, and / or the SAP.

***Section 7.3.5.1 Quantitated bone scan endpoints:***

Added text:

Further details will be defined in the imaging charter and / or related central review documentation, and / or the SAP.

**Change 23:**

***Section 7.1.1 Tabulated overview, Table 7-1 Schedule of procedures:***

See **Change 26.**

***Section 7.1.2.1 Screening period*** (paragraph 2, 8th bullet, 2nd sub-bullet);

***Section 7.1.2.2 Initial visit-Dose 1, Day 1 (Treatment Arms A, B, and C)*** (paragraph 1, 6th bullet, 2nd sub-bullet):

***Section 7.1.2.3 Doses 2 to 6 (Treatment Arms A and B)*** (paragraph 1, 4th bullet, 2nd sub-bullet);

***Section 7.1.2.4 Doses 2 to 12 (Treatment Arm C)*** (paragraph 1, 4th bullet, 2nd sub-bullet);

***Section 7.1.2.5 End of treatment visit*** (paragraph 1, 4th bullet, 2nd sub-bullet);

***Section 7.1.2.6.1 Active follow-up with clinic visits*** (paragraph 3, 4th bullet, 2nd sub-bullet);

***Section 7.1.2.7.1 End of active follow-up with clinic visits*** (paragraph 1, 2nd bullet, 2nd sub-bullet)

***Section 7.5 Safety*** (paragraph 1, 2nd bullet, 2nd sub-bullet); and

***Section 7.5.3.1 Laboratory evaluations*** (paragraph 1, 2nd bullet):

Added text:

- Chemistry panel, including serum creatinine, sodium, potassium, chloride, calcium, phosphorous, magnesium, total bilirubin.....

**Change 24:**

***Synopsis - Diagnosis and main criteria for inclusion*** (paragraph 2) **and**

***Section 5.1.1 inclusion criteria*** (paragraph 1):

4th bullet:

Old text:

- Eastern Cooperative Oncology Group performance status (ECOG PS) 0 to 2. In case of ECOG PS 2, the PS ~~has to~~ be due to metastatic prostate cancer to the bone.

New text:

- Eastern Cooperative Oncology Group performance status (ECOG PS) 0 to 2. In case of ECOG PS 2, the PS must be due to metastatic prostate cancer to the bone.

7th bullet, “d”:

Added text:

- d. Total bilirubin level  $\leq 1.5 \times$  institutional upper limit of normal (ULN) ( $< 3 \times$  ULN for subjects with documented Gilbert’s syndrome)

***Synopsis - Plan for statistical analysis:***

Last paragraph:

Old text:

The following secondary efficacy time-to-event endpoints will have hypothesis testing performed to ~~compare the treatment groups~~: OS, time to first SSE, time to radiological progression, and rPFS. Other endpoints, including safety and tolerability variables, will be analyzed descriptively for each treatment group.

New text:

Comparison 2 will be performed using a log-rank test with a 1-sided alpha of 0.1 stratified by the randomization factors (previous chemotherapy [ $\leq 1$  regimen versus  $> 1$  regimen] and total ALP [ $< 220$  U/L versus  $\geq 220$  U/L]). The extended dosing regimen will be declared superior to the standard dosing regimen if the 1-sided p-value from the stratified log rank test is less than 0.1.

The following secondary efficacy time-to-event endpoints will have hypothesis testing performed with comparisons analogous to those for the primary endpoint: OS, time to first SSE, time to radiological progression, and rPFS. Other endpoints, including safety and tolerability variables, will be analyzed descriptively for each treatment group.

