### ***Section 8.1 General considerations***

Paragraph 2, 3rd bullet:

New text:

- Average WPS of the BPI-SF (WPS  $\leq 4$  versus WPS  $>4$ )

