- l. The randomization will be permuted-block, stratified by the use of prior chemotherapy ( $\leq 1$  regimen versus  $> 1$  regimen), by total alkaline phosphatase ( $< 220$  U/L versus  $\geq 220$  U/L), and by average WPS of the BPI-SF (WPS  $\leq 4$  versus WPS  $> 4$ ). This assessment will occur when the second call is made to the IVRS / IWRS to order drug:  $\geq 10$  to 14 days prior to study treatment administration.
- m. The BPI-SF questionnaire will be completed at each clinic visit from Dose 1, Day 1 until the Week 48 visit and for Treatment Arms A and B only, on the day of each telephone contact at Weeks 28, 32, 40 and 44. For further details, see Section 14.7.
- n. Prior to randomization, the subject will use the hand-held device to complete selected questions from the BPI-SF questionnaire, Question 3, worst pain in the last 24 hours will be completed for at least 4 days during a period of no more than 1 week prior to randomization. The average of the 4 days will be used as the randomization stratification value.
- o. Twenty-four (24)-hour analgesic use will be collected and it will be assessed by the study investigator until the Week 48 visit. Twenty-four (24)-hour analgesic use will also be collected by the study investigator at each telephone contact (in Arms A and B) or visit at Weeks 28, 32, 40, and 44.

- p. Systolic / diastolic blood pressure, respiratory rate, body temperature, and heart rate will be measured after the subject has rested for at least 5 minutes.
- q. After a complete physical examination at screening, subsequent physical examinations may be 'brief,' but should include any systems with symptoms. All physical examinations will be performed by a physician according to the standard of care.
- r. Complete blood count, including hematocrit, hemoglobin, red blood cell count, mean corpuscular volume, mean corpuscular hemoglobin, mean corpuscular hemoglobin concentration, white blood cell count, platelet count, and differential blood count reported as absolute count or percentage for neutrophils, lymphocytes, monocytes, eosinophils, and basophils will be collected. Chemistry panel including serum creatinine, sodium, potassium, chloride, calcium, phosphorous, magnesium, total bilirubin, total alkaline phosphatase, aspartate transaminase, alanine transaminase, lactate dehydrogenase (screening only), and albumin (screening only).

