**Change 5:**

Updated analysis for Comparison 2 from 24 weeks to 6th dose date

Sections affected included:

- Synopsis-Study objectives
- Synopsis-Plan for statistical analysis
- 2.0 Study objectives
- 4.4 End of study
- 7.3.2 Definition of efficacy variables
- 7.3.5.6 Additional pain and health related quality of life endpoints
- 8.2 Analysis sets
- 8.4.1 Primary efficacy analysis
- 8.4.2.2 Analyses of standard dosing and extended dosing from the 6th dose date
- 8.6 Determination of sample size

*Rationale:* The 'Week 24 baseline value' is defined as the last non-missing value on or before the date of the 6th injection. Ideally, this visit would be the date of the 7th injection for Arm C subjects and expected 7th injection date for Arm A subjects. However, the end of treatment visit (30±7 days from last dose) for Arm A subjects could be missing due to consent withdrawal or happen out of visit window. Hence, there is no comparable visit for Arm A subjects that could be used as the expected 7th injection date. To account for this and

achieve comparability between the two arms, the 6th injection date is used as the reference date for Comparison 2 subjects.

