#### **8.6 Determination of sample size**

Old text:

Comparison 2 will analyze SSE-FS from ~~24 weeks~~ in subjects surviving SSE-free to ~~24 weeks completing and / or without prior permanent discontinuation from treatment.~~(27,28) A median SSE-FS of 9 months with constant hazards is assumed for standard dose. Extended dosing is assumed to have the same SSE-FS efficacy as standard dosing for the first 24 weeks, and 65% improvement (hazard ratio 0.606) thereafter. With 240 of 360 subjects randomized to Treatment Arm A and Treatment Arm C, simulations indicated that 44.65% of randomized subjects (107.2 of 240) would have an SSE-FS event or loss to follow-up during the first 24 weeks, leaving an estimated 55.35% (132.8) surviving SSE-free and eligible for inclusion at 24 weeks. An average of 74.9 simulated events occurred for this comparison, and a 1-sided log-rank test with 0.10 significance gave approximately 80.6% power to test H02 versus HA2.

New text:

Comparison 2 will analyze SSE-FS from the 6th dose, in subjects surviving SSE-free to the 6th dose.(27,28) A median SSE-FS of 9 months with constant hazards is assumed for standard dose. Extended dosing is assumed to have the same SSE-FS efficacy as standard dosing for the first 24 weeks, and 65% improvement (hazard ratio 0.606) thereafter. With

240 of 360 subjects randomized to Treatment Arm A and Treatment Arm C, simulations indicated that 44.65% of randomized subjects (107.2 of 240) would have an SSE-FS event or loss to follow-up during the first 24 weeks, leaving an estimated 55.35% (132.8) surviving SSE-free and eligible for inclusion at 24 weeks. An average of 74.9 simulated events occurred for this comparison, and a 1-sided log-rank test with 0.10 significance gave approximately 80.6% power to test H02 versus HA2.

## Change 6

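### Comparison 2 starts at the 6th dose but is stratified only by factors recorded at randomization; adding ALP and worst pain at the 6th-dose baseline as covariates would improve precision at almost no cost

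*Protocol*

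**What the plan says.** **Decision test.** The Amendment 1 text for the synopsis (Plan for statistical analysis) reads: "Comparison 2 will be performed using a log-rank test with a 1-sided alpha of 0.1 stratified by the randomization factors". The factors listed are prior chemotherapy (≤1 versus >1 regimen) and total ALP (<220 versus ≥220 U/L). Superiority is declared if the one-sided p-value is below 0.1.

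**Time zero.** After Amendment 3, Section 8.6 says: "Comparison 2 will analyze SSE-FS from the 6th dose, in subjects surviving SSE-free to the 6th dose". The changes listed for Amendment 3 do not touch the strata, and the Amendment 4 overview lists no statistical change.

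**Pain at randomization.** Amendment 1 made average WPS (≤4 versus >4) a third randomization factor and added "Average WPS of the BPI-SF" to the list in Section 8.1. The Comparison 2 strata named in the synopsis text do not include it.

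**Values at the 6th dose.** Table 7-1 schedules the chemistry panel at each dosing visit, and footnote r lists "total bilirubin, total alkaline phosphatase, aspartate transaminase, alanine transaminase, lactate dehydrogenase (screening only" among its components. The results must be available before dosing. Sections 7.1.2.4 and 7.1.2.5 have subjects rate pain daily for the week ending on the morning of each dosing visit. The rationale for Amendment 3, Change 5 says that the Week 24 baseline value "is defined as the last non-missing value on or before the date of the" 6th injection.

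**Design figures.** Section 8.6 gives "A median SSE-FS of 9 months with constant hazards is assumed for standard dose" and, for extended dosing after the first 24 weeks, "65% improvement (hazard ratio 0.606) thereafter". It expects 132.8 of 240 subjects to enter Comparison 2, 74.9 events and 80.6% power.

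**The concern.** The strata describe subjects as they were at screening. Comparison 2 describes them from the 6th dose, after five injections of a drug expected to change ALP: Section 7.3.5.3.1 defines an ALP response as a confirmed fall of at least 30%. A screening ALP category may therefore be a poor guide to risk at time zero, and pain does not enter the named strata at all.

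The comparison is small (about 75 events, power near 80%), and its set is formed after randomization, with about 45% of Arms A and C expected to drop out first. Two values likely to carry prognostic information are on file at the comparison's own baseline and are not used in the decision test. What is at stake is some precision, possibly some power, and chance imbalance in these values at time zero, which stays in the estimate.

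**Working it through.** **1. The plan's own power.** Inputs from Section 8.6 and the synopsis: D = 74.9 events, HR = 0.606, one-sided alpha 0.10 (z = 1.2816). Equal allocation between Arms A and C is assumed.

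- Schoenfeld: Φ(|ln 0.606| × √(74.9/4) − 1.2816) = Φ(0.501 × 4.327 − 1.2816) = Φ(0.886) = 81.2%.
- Freedman: Φ(√74.9 × (1 − 0.606)/(1 + 0.606) − 1.2816) = Φ(8.654 × 0.2453 − 1.2816) = Φ(0.842) = 80.0%.

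The stated 80.6% lies between the two, so it reproduces.

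**2. Age of the strata at time zero.** Dose 6 is scheduled five intervals after Dose 1: 5 × 28 = 140 days, or 20 weeks. Footnote d of Table 7-1 allows 28 ± 7 days per interval, so the earliest is 5 × 21 = 105 days, or 15 weeks. Section 7.1.2.2 allows up to 28 further days from randomization to Dose 1.

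**3. Whether 6th-dose values are legitimate covariates.** Arms A and C have the same planned dose and schedule up to Dose 6 (Section 7.1.2.2). A value on or before the 6th injection therefore precedes any planned difference in treatment.

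**4. Effect on power.** The documents give neither the prognostic strength of 6th-dose ALP and pain nor their correlation with the randomization values. Both were varied in simulation:

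- 133 subjects, 1:1, exponential times with a 9-month control median, 18-month uniform entry (assumed), analysis at 75 events, 4,000 runs per setting.
- Correlation of randomization and 6th-dose values 0.4 to 0.8.
- Planned test: log-rank stratified by chemotherapy and ALP category at randomization.
- Alternative: Cox model with the same strata plus continuous 6th-dose ALP and pain.

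Ranges below run over the three correlations. Strength is log-hazard per SD (ALP / pain).

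| Strength | 0.606 conditional: planned → Cox | Change, points | 0.606 marginal: planned → Cox | Change, points |
|---|---|---|---|---|
| 0 / 0 | 78–79% → 78–79% | −0.5 to −0.1 | 79–80% → 78–80% | −1.1 to −0.4 |
| 0.2 / 0.1 | 78% → 78–79% | +0.3 to +0.7 | 79–81% → 79–82% | +0.7 to +1.0 |
| 0.3 / 0.2 | 75–77% → 78–79% | +1.5 to +2.6 | 80–82% → 82–84% | +1.6 to +2.4 |
| 0.4 / 0.3 | 72–75% → 78–79% | +3.7 to +5.5 | 80–81% → 85% | +3.8 to +5.1 |
| 0.6 / 0.4 | 68–71% → 78–80% | +7.6 to +11.9 | 80–82% → 89–90% | +6.9 to +9.1 |

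The 0 / 0 rows are the same setting run twice, so they differ only by simulation error. Replacing the strata with dichotomised 6th-dose ALP and pain does less: about −3 to +6 points.

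**5. Validity.** Under the null, the planned test rejected in 9.8% of 8,000 runs, against a nominal 10%. In a separate simulation with one 6th-dose covariate in the Cox model, rejection was 10.2%.

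**6. Chance imbalance at time zero.** With 133 subjects split 1:1, the standard error of a difference in covariate means is √(4/133) = 0.173 SD. A one-standard-error imbalance shifts the log HR by 0.173 × 0.3 = 0.05, 0.173 × 0.5 = 0.09 or 0.173 × 0.7 = 0.12 at assumed strengths of 0.3, 0.5 and 0.7 per SD. For scale, the design log HR is 0.50 and its standard error is about √(4/75) = 0.23.

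**The case against.** A log-rank test stratified by randomization factors is standard and valid, and an adjusted Cox model is ordinary SAP content. Neither the SAP nor the current Sections 8.1 and 8.4.1 are at hand, so nobody can say from this document that no other adjustment is planned. That stands. It does not remove the point: the synopsis text fixes the decision test itself, and a supportive model in the SAP would leave that decision unchanged.

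Three stronger readings are tempting, and the documents support none of them.

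- **That the plan is short of power by a known amount.** The size depends wholly on assumed prognostic strength, and the range includes zero. Section 8.6 states 0.606 beside a 9-month median and constant hazards, with no covariates, which reads most naturally as a marginal effect. On that reading the planned test keeps about 79–82% power in every setting. The gap between marginal and conditional hazard ratios is non-collapsibility, not bias.
- **That the arms are unbalanced at the 6th dose because of selection.** Planned treatment is identical until then, and nothing shown indicates that entry to the set differs by arm. Chance imbalance does not inflate type I error. If selection did differ, two covariates would correct it only in part.
- **That the strata are always at least 20 weeks old.** Twenty weeks after Dose 1 is nominal; the visit windows allow 15.

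It is also fair to say that a covariate-adjusted decision test adds modelling assumptions that the log-rank test does not need.

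**Conclusion.** The point holds as a recommended improvement, not as an error. The named strata for Comparison 2 date from randomization, pain is not among them, and usable ALP and pain values exist at the comparison's own baseline.

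The Cox model with both covariates changes power by about −1 to +1 point if they are weakly prognostic, and by about +1.5 to +12 points if mildly to strongly prognostic. The realistic downside is therefore about one point. These figures rest on assumed strengths of 0 to 0.6 (ALP) and 0 to 0.4 (pain) per SD, correlations of 0.4 to 0.8, and an assumed entry pattern. If 0.606 is marginal, the change is a gain over the stated 80.6%.

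Adjustment would also remove chance imbalance in these two values, worth about 0.05 to 0.12 on the log HR scale for a one-standard-error imbalance at strengths of 0.3 to 0.7 per SD.

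**What to change.** For Comparison 2:

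- Keep the stratification by randomization factors, and confirm whether WPS is meant to be one of the strata.
- Pre-specify a Cox model with those strata, treatment, log total ALP and 7-day mean WPS. Take both covariates at the 6th-dose baseline, under the rule already written: last non-missing value on or before the 6th injection. Report the adjusted hazard ratio with 80% and 95% confidence intervals.
- Choose the role of this model before analysis. If the power gain is wanted, make its one-sided score test for treatment the decision test. Otherwise make it the key supportive analysis, which sharpens the estimate but leaves the power of the log-rank decision unchanged.
- State that both values precede any planned difference in treatment between Arms A and C.

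The cost is wording in the protocol and SAP; no new data are needed. In return, the adjusted hazard ratio is conditional on the two covariates and assumes a log-linear effect of each.

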***Section 6.4.7 Dose delays:***

Under Myelosuppression, paragraph 1, 4th bullet:

Added text:

- Blood transfusions are acceptable during the treatment period, but erythropoietin is not allowed. Use of biologic response modifiers, such as GM-CSF or G-CSF, is allowed in the management of acute toxicity during the treatment period. Such drugs (and transfusions) cannot be used for 4 weeks prior to screening and during the screening period, or prior to the start of treatment.

**Section 7.1.1 Tabulated overview, Table 7-1 Schedule of procedures** (footnote “o”);  
**Section 7.1.2.2 Initial visit-Dose 1, Day 1 (Treatment Arms A, B, and C)** (paragraph 1, 13th bullet);  
**Section 7.1.2.3 Doses 2 to 6 (Treatment Arms A and B)** (paragraph 1, 10th bullet);  
**Section 7.1.2.4 Doses 2 to 12 (Treatment Arm C)** (paragraph 1, 10th bullet);  
**Section 7.1.2.5 End of treatment visit** (paragraph 1, 10th bullet); and  
**Section 7.1.2.6.1 Active follow-up with clinic visits** (paragraph 3, 9th bullet);

Revised text from “treating physician” to “study investigator”.

**Section 7.1.1 Tabulated overview, Table 7-1 Schedule of procedures:**

Footnotes “i”, “j”, and “k”: added text:

“using a handheld device”, see **Change 26**.

**Section 7.1.2.2 Initial visit-Dose 1, Day 1 (Treatment Arms A, B, and C)** (paragraph 1, 2nd bullet);  
**Section 7.1.2.3 Doses 2 to 6 (Treatment Arms A and B)** (paragraph 1, 1st bullet);  
**Section 7.1.2.4 Doses 2 to 12 (Treatment Arm C)** (paragraph 1, 1st bullet); and  
**Section 7.1.2.5 End of treatment visit** (paragraph 1, 1st bullet):

Added text:

- BPI-SF questionnaire using a handheld device (should be self-administered at the beginning of each visit through Week 48 and should be checked for completion at the visit; see Section 14.7).

**Section 7.1.2.6.1 Active follow-up with clinic visits:**

Paragraph 3, 1st sentence:

Added text:

The following assessments will be performed during the clinic visits:

Paragraph 9:

Added text:

If a subject is no longer able to travel to the clinic due to deteriorating status, the subject will enter the active follow-up without visits and will be followed by telephone.

Paragraph 10:

Old text:

If a subject has a SSE in the active ~~safety~~-follow-up period, he will continue the ~~2-year~~ active ~~safety~~ follow-up period.

New text:

If a subject has an SSE in the active follow-up period, he will continue the active follow-up period for 2 years from last study treatment. If a subject becomes unable to travel to the clinic after 2 years after his last treatment, he will enter long-term follow-up.

### ***Section 7.3.2 Definition of efficacy variables***

Paragraph 1, 2nd sentence:

Added text:

Response and progression endpoints are defined with respect to 2 corresponding baselines, the screening (or pre-treatment) baseline and 24 weeks.

### ***Section 7.2.5.5 Additional pain and health-related quality of life endpoints:***

Revised title of section:

Added text:

7.3.5.5 Additional pain and health related quality of life endpoints

### ***Section 8.4.2.1 Analyses of pooled standard dose and high dose from randomization***

Paragraph 1, 2nd sentence:

Added text:

For these analyses, the start date will be randomization, and the screening (or pre-treatment) baseline will be used.

### ***Section 8.4.4 Safety analysis:***

Paragraph 5, 3rd subsection:

Added text:

3. Safety events emerging following the standard-regimen treatment period

This analysis will be performed in each treatment arm for events following the later of 24 weeks from treatment start or 30 days following completion of 6 doses of radium 223 dichloride treatment. It will be performed for selected safety endpoints collected during active follow-up after end of treatment through primary endpoint completion. This analysis will be performed by treatment group as treated.

